## 8. STATISTICAL METHODS AND ANALYSES

### 8.1. Statistical Methods

#### 8.1.1. Continuous variables

For continuous variables, summary statistics (number of patients [n], mean, standard deviation, median, maximum, and minimum) will be calculated. For body surface area, quartiles (first and third quartiles) will also be calculated.

#### 8.1.2. Categorical variables

For categorical variables, results of each categorization will be summarized in terms of frequency and proportion.

#### 8.1.3. Binary variables

For binary variables, patients falling into each binary category will be summarized in terms of frequency (n) and proportion. If a confidence interval (CI) is determined for a proportion, the two-sided 95% CI will be determined using the exact method.

For a comparison of proportion between subgroups, the risk ratio (RR) and its 95% CI will be determined. In addition, the RRs and their 95% CIs will be graphically presented.

For statistical tests, Fisher's exact test will be performed to test correlations in nominal scale data, and Cochran-Armitage test (exact method) to test correlations in ordinal scale data. If, however, it is difficult to use the exact method, chi-square test or Cochran-Armitage test with normal approximation will be used as an alternative to the exact method.

#### 8.1.4. Time-to-event data

For time-to-event data, the median, 1st quartile, and 3rd quartile will be determined using the Kaplan-Meier method. The rate at each time point will also be determined. To estimate CIs, log-log transformation will be used (this corresponds to specifying loglog under the conftype option in the proc lifetest statement of the SAS® lifetest procedure). In addition, Kaplan-Meier plots will be presented.

When time data are compared between subgroups using the Kaplan-Meier method, the hazard ratio of event occurrence and its 95% CI will be determined using the Cox proportional hazards model (ties handled by the Breslow method). In addition, the hazard ratio and its 95% CI will be presented graphically.

In the analysis of time data with competing risks, the cumulative incidence rate at each time point that takes into account competing risks will be determined (this corresponds to using the event code option in the time statement of the SAS® lifetime procedure). The standard error is to be estimated by the delta method. In addition, the time course of cumulative incidence will be graphically presented.

## 8.2. Statistical Analyses

Analyses similar to those in the SAS and the EAS will also be performed in the SASIC and the EASIC; details of these analyses will be separately specified. When performing these analyses, the SAS and the EAS should be read as the SASIC and the EASIC, respectively.

### 8.2.1. Summary of patients

- **Disposition**

The registered patients, survey-completed patients, patients included in the SAS, and patients included in the EAS will be counted in the population of registered patients. In addition, case report form-uncollected patients, patients excluded from the SAS, and patients excluded from the EAS will also be counted. For those excluded from the SAS/EAS, patients will also be counted by reason for exclusion.

- **Follow-up period**

For the SAS and EAS, the follow-up period after the start of this drug and the follow-up period after HSCT will be analyzed.

- For the follow-up period (weeks) after the start of this drug:
  - Patients included in the analysis: The SAS and the EAS
  - Subgroup analyses: In addition to the summary with all patients in each analysis set above, patients will also be summarized by the conditions where patients underwent HSCT after the start of this drug and patients did not.
  - What are analyzed:
    - ◊ Summary statistics for the follow-up period (calculated as per Section 8.1.1)
    - ◊ Number of patients by follow-up duration (< 12 weeks, ≥ 12 weeks to < 24 weeks, every 12 weeks thereafter; and < 13 weeks, ≥ 13 weeks to < 26 weeks, and every 13 weeks thereafter) (calculated as per Section 8.1.2)
    - ◊ Number of patients who were being followed up at each time point (Week 12, Week 24, and every 12 weeks thereafter; and Week 13, Week 26, and every 13 weeks thereafter) (calculated as per Section 8.1.2)
- For follow-up period after HSCT (weeks) = follow-up period after the first HSCT after the start of this drug:
  - Patients included in the analysis: patients in the SAS/EAS who underwent HSCT after the start of this drug
  - What are analyzed: Same as those for the follow-up period after the start of this drug

- **Summary of patients with completed/discontinued status**

For the SAS and EAS, patients with the following kinds of completed/discontinued status will be summarized in terms of n and proportion by timing. In addition, patients will also be summarized in terms of n and proportion by reason. To calculate the proportion of patients falling into each reason in each timing, the number of patients who completed or discontinued treatment/survey in the relevant timing will be used as the denominator.

#### **Completion/discontinuation of treatment**

Definition of the timing 1 of completion/discontinuation of treatment: < 4 weeks after the start of this drug,  $\geq$  4 weeks to < 8 weeks,  $\geq$  8 weeks to < 12 weeks,  $\geq$  12 weeks to < 16 weeks,  $\geq$  16 weeks to < 20 weeks,  $\geq$  20 weeks to < 24 weeks,  $\geq$  24 weeks, entire period

Definition of the timing 2 of completion/discontinuation of treatment: Cycle 1 ongoing or started but the next cycle not started, the same with Cycle 2, the same with Cycle 3, the same with Cycle 4, the same with Cycle 5, the same with Cycle 6, after the start of the subsequent cycle, entire period

#### **Continuation/discontinuation of survey (treatment period and follow-up period)**

Definition of the timing 1: < 4 weeks after the start of this drug,  $\geq$  4 weeks to < 8 weeks,  $\geq$  8 weeks to < 12 weeks,  $\geq$  12 weeks to < 16 weeks,  $\geq$  16 weeks to < 20 weeks,  $\geq$  20 weeks to < 24 weeks,  $\geq$  24 weeks to < 52 weeks,  $\geq$  52 weeks, entire period

Definition of the timing 2: < 4 weeks after the end of this drug,  $\geq$  4 weeks to < 12 weeks,  $\geq$  12 weeks to < 24 weeks,  $\geq$  24 weeks to < 48 weeks,  $\geq$  48 weeks, entire period

- Transfer to another hospital**

A patient is defined to have been transferred, if the patient's information at the transferred hospital is linked to the patient's information at the original hospital through the case report form prepared at the transferred hospital. For the SAS and EAS, patients will be summarized by each of the following factors, as per Section 8.1:

- Transfer to another hospital [absent, present]
- Timing of transfer (treatment period, follow-up period) \* The timing will be determined referring to the record of survey continuation/discontinuation in the original hospital's case report form. The denominator will be the number of patients with transfer.

- Summary of excluded patients**

Patients excluded from the SAS, those excluded from the EAS, and reasons for exclusion will be listed.

#### **8.2.2. Patient characteristics and treatment history**

- Patient characteristics**

For the SAS and EAS, patients will be summarized by each of the following patient characteristics, as per Section 8.1:

- Sex [male, female]
- Age (continuous)
- Age [ $< 15$  years,  $\geq 15$  years,  $\geq 15$  years to  $< 65$  years,  $\geq 65$  years]
- Age [ $< 18$  years,  $\geq 18$  years,  $\geq 18$  years to  $< 55$  years,  $\geq 55$  years]
- Age [ $< 15$  years,  $\geq 15$  years,  $\geq 15$  years to  $< 40$  years,  $\geq 40$  years]
- Body surface area (continuous)
- Disease name [Relapsed or refractory CD22+ acute lymphocytic leukemia (ALL), relapsed CD22+ ALL, refractory CD22+ ALL, other ALL, other, individual names included in the "other"]
- WHO classification [B-lymphoblastic leukemia/lymphoma, unspecified type, B-lymphoblastic leukemia/lymphoma with recurrent gene abnormalities, T-lymphoblastic leukemia/lymphoma, other, individual names included in the "other"]
- Chromosome karyotype [normal, abnormal, unknown]\* Chromosome karyotype is to be considered abnormal if any of the following conditions is met: t (9; 22), t (4; 11), Complex, Karyotype (5 or more chromosomal abnormalities), other
- Chromosome karyotype [normal, t (9; 22), t (4; 11), Complex, Karyotype (5 or more chromosomal abnormalities), other, unknown]
- Chromosome karyotype [Philadelphia chromosome positive, negative, unknown]\* Philadelphia chromosome is considered positive if the chromosome karyotype is t(9;22).
- Disease duration [ $< 3$  months,  $\geq 3$  months to  $< 6$  months,  $\geq 6$  months to  $< 9$  months,  $\geq 9$  months to  $< 12$  months (1 year),  $\geq 1$  year to  $< 2$  years,  $\geq 2$  years]
- Hepatic impairment [absent, present] (According to the Procedure of Extracting Patients with Hepatic Impairment/Renal Impairment in Post-Marketing Surveillance and its Attachment, the MedDRA version used for analysis should be followed.)
- Renal impairment [absent, present] (According to the Procedure of Extracting Patients with Hepatic Impairment/Renal Impairment in Post-Marketing Surveillance and its Attachment, the MedDRA version used for analysis should be followed.)
- Medical history (past) [absent, present]
- Medical history (past) - VOD/SOS [absent, present]
- Medical history (past) - GVHD [absent, present]
- Medical history (past) - Hepatitis or hepatic disease [absent, present]
- Medical history (present) [absent, present]
- Medical history (present) - VOD/SOS [absent, present]
- Medical history (present) - GVHD [absent, present]
- Medical history (present) - Hepatitis or hepatic disease [absent, present]
- ECOG PS before the start of this drug [0, 1, 2, 3, 4, not performed]
- ECOG PS before the start of this drug [0, 1,  $\geq 2$ , not performed]
- AST level immediately before the start of this drug [ $\leq 1.5 \times$  the institutional upper limit normal range (IULN),  $> 1.5 \times$  IULN, not performed]
- ALT level immediately before the start of this drug [ $\leq 1.5 \times$  IULN,  $> 1.5 \times$  IULN, not performed]
- AST and ALT levels immediately before the start of this drug [ $\leq 1.5 \times$  IULN, either  $> 1.5 \times$  IULN, not performed]
- $\gamma$ -GTP level immediately before the start of this drug [ $\leq 50$  IU/L,  $> 50$  IU/L, not performed]
- Total bilirubin level immediately before the start of this drug [ $\leq$  IULN,  $>$  IULN, not performed]

- Hemoglobin level immediately before the start of this drug [ $< 10 \text{ g/dL}$ ,  $\geq 10 \text{ g/dL}$ , not performed]
- Platelet count immediately before the start of this drug [ $< 10 \times 10^4/\mu\text{L}$ ,  $\geq 10 \times 10^4/\mu\text{L}$ , not performed]
- Peripheral blast count immediately before the start of this drug [ $\leq 1000/\mu\text{L}$ ,  $> 1000/\mu\text{L}$ , not performed]
- Myeloblast count immediately before the start of this drug [ $\leq 50\%$ ,  $> 50\%$ , not performed]
- Salvage line of the induction treatment with this drug [Initial induction, 1st, 2nd, 3rd or later]

For the SAS, patients falling into the following categories will be summarized in terms of n and proportion by System Organ Class (SOC) and Preferred Term (PT):

- Medical history (past)
- Medical history (past) - hepatitis or hepatic disease
- Medical history (present)
- Medical history (present) - hepatitis or hepatic disease

For the SAS and EAS, patients falling into the following categories defined for HSCT performed before the start of this drug will be summarized in terms of n and proportion. Note that only patients who underwent HSCT before the start of this drug will be included in this summary, except for "HSCT before the start of this drug [not performed, performed]":

- HSCT before the start of this drug [not performed, performed]
- Number of HSCTs before the start of this drug [1,  $\geq 2$ ]
- Type of HSCT before the start of this drug (regardless of the number of HSCTs) [autologous transplant, allogeneic hematopoietic stem cell transplant with myeloablative conditioning, allogeneic hematopoietic stem cell transplant with nonmyeloablative conditioning, unknown]
- Type of the HSCT immediately before the start of this drug [same as above]
- Type of the conditioning drug for HSCT before the start of this drug (regardless of the number of HSCTs) [busulfan (BSF, BUS), cyclophosphamide (CPA), melphalan (LPAM), cytarabine (Ara-C), fludarabine phosphate (F-ara-AMP), etoposide (ETP, VP-16), other]
- Type of the conditioning drug for the HSCT immediately before the start of this drug [same as above]
- Time from the date of the HSCT immediately before the start of this drug to the date of the start of this drug (continuous)

Listings will also be prepared.

For the SAS and EAS, patients falling into the following categories defined for remission induction therapies performed before the start of this drug will be summarized in terms of n and proportion. Note that only patients who received remission induction therapy before the start of this drug will be included in this summary, except for "Remission induction chemotherapy before the start of this drug [not performed, performed]":

- Remission induction chemotherapy before the start of this drug [not performed, performed]

- Induction chemotherapy regimen and response before the start of this drug (regardless of line of therapy)
- Regimen of the induction chemotherapy immediately before the start of this drug (by line of treatment)
- Regimen and response of the induction chemotherapy immediately before the start of this drug

For the SAS and EAS, summary will be performed for anti-malignant tumor agents (drug code 42x) started by the day of the final dose of this drug that are recorded as concomitant anti-malignant tumor agents used for the target disease. Listings will also be prepared.

For the SAS and EAS, patients falling into the following categories defined for HSCT performed after the start of this drug will be summarized in terms of n and proportion. Note that only patients who underwent HSCT after the start of this drug will be included in this summary, except for "HSCT after the start of this drug [not performed, performed]":

- HSCT after the start of this drug [not performed, performed]
- Number of HSCTs after the start of this drug [1,  $\geq 2$ ]
- Type of HSCT after the start of this drug (regardless of the number of HSCTs) [autologous transplant, allogeneic hematopoietic stem cell transplant with myeloablative conditioning, allogeneic hematopoietic stem cell transplant with nonmyeloablative conditioning, unknown]
- Type of the first HSCT after the start of this drug [same as above]
- Donor of HSCT after the start of this drug (regardless of the number of HSCTs) [alternative donor, matched related donor]
- Donor of the first HSCT after the start of this drug [same as above]
- Type of conditioning drug for HSCT after the start of this drug (regardless of the number of HSCTs) [busulfan (BSF, BUS), cyclophosphamide (CPA), melphalan (LPAM), cytarabine (Ara-C), fludarabine phosphate (F-ara-AMP), etoposide (ETP, VP-16), other]
- Type of conditioning drug for the first HSCT after the start of this drug [same as above]
- Conditioning with alkylating agent for the first HSCT after the start of this drug [ $\leq 1$  agent (including no conditioning),  $\geq 2$  agents]
- Conditioning with busulfan for the first HSCT after the start of this drug [not performed (including no conditioning), performed]
- ECOG PS before conditioning for the first HSCT after the start of this drug [0, 1, 2, 3, 4, not performed]
- ECOG PS before conditioning for the first HSCT after the start of this drug [0, 1,  $\geq 2$ , not performed]
- AST level before conditioning of the first HSCT after the start of this drug [ $\leq 1.5 \times$  the institutional upper limit of normal range (IULN),  $> 1.5 \times$  IULN, not performed]
- ALT level before conditioning of the first HSCT after the start of this drug [ $\leq 1.5 \times$  IULN,  $> 1.5 \times$  IULN, not performed]
- AST and ALT levels before conditioning for the first HSCT after the start of this drug [ $\leq 1.5 \times$  IULN, either  $> 1.5 \times$  IULN, not performed]
- $\gamma$ -GTP level before conditioning for the first HSCT after the start of this drug [ $\leq 50$  IU/L,  $> 50$  IU/L, not performed]

- Total bilirubin level before conditioning for the first HSCT after the start of this drug [ $\leq$  IULN,  $>$  IULN, not performed]
- Hemoglobin level before conditioning for the first HSCT after the start of this drug [ $< 10$  g/dL,  $\geq 10$  g/dL, not performed]
- Platelet count before conditioning for the first HSCT after the start of this drug [ $< 10 \times 10^4/\mu\text{L}$ ,  $\geq 10 \times 10^4/\mu\text{L}$ , not performed]
- Peripheral blast count before conditioning for the first HSCT after the start of this drug [ $\leq 1000 / \mu\text{L}$ ,  $> 1000 / \mu\text{L}$ , not performed]
- Myeloblast count before conditioning for the first HSCT after the start of this drug [ $\leq 50\%$ ,  $> 50\%$ , not performed]
- Time from the start date of this drug to the date of the first HSCT after the start of this drug (continuous)
- Time from the start date of this drug to the date of the first HSCT after the start of this drug [ $< 4$  weeks,  $\geq 4$  weeks to  $< 8$  weeks,  $\geq 8$  weeks to  $< 12$  weeks,  $\geq 12$  weeks to  $< 16$  weeks,  $\geq 16$  weeks to  $< 20$  weeks,  $\geq 20$  weeks to  $< 24$  weeks,  $\geq 24$  weeks to  $< 28$  weeks,  $\geq 28$  weeks]
- Time from the date of final dose of this drug to the date of the first HSCT after the start of this drug (continuous)
- Time from the date of final dose of this drug to the date of the first HSCT after the start of this drug [ $< 4$  weeks,  $\geq 4$  weeks to  $< 8$  weeks,  $\geq 8$  weeks to  $< 12$  weeks,  $\geq 12$  weeks to  $< 16$  weeks,  $\geq 16$  weeks to  $< 20$  weeks,  $\geq 20$  weeks to  $< 24$  weeks,  $\geq 24$  weeks]

Data for the time from the start of this drug to the first HSCT after the start of this drug will be summarized in a histogram with the 1st class being from 0 to 4 weeks and a class width of 4 weeks thereafter (the longitudinal axis is frequency). Data for the time from the date of final dose of this drug to the first HSCT after the start of this drug will also be summarized in the same manner. Listings concerning HSCT will also be prepared.

For the SAS and EAS, patients will be summarized in terms of n and proportion by each of the following factors:

- Individual drug therapies for the target disease (started by the end of the treatment period [i.e., by Day 28 post-final dose])
- Prophylactic injection to reduce infusion reactions [not performed, performed]
- Prophylactic treatment to prevent/reduce tumor lysis syndrome [not performed, performed]
- **Relationship between age and patient characteristics**

For the patient population aged 15 years or older, patients aged 65 years or older will be summarized in terms of n and proportion by each of the following factors selected from those specified in Section 5.4. In addition, statistical testing and risk ratio estimation will be performed according to Section 8.1.3.

- Hepatic impairment
- Medical history (past) - Hepatitis or hepatic disease
- Medical history (present) - Hepatitis or hepatic disease
- AST and ALT levels immediately before the start of this drug

- $\gamma$ -GTP level immediately before the start of this drug
- Salvage line of the induction treatment with this drug
- HSCT before the start of this drug

Similar analysis will be performed for patients aged < 15 years in the patient population aged < 65 years.

- **Status of the treatment with this drug**

For the SAS, status of the treatment with this drug will be summarized with respect to the following factors. Similar summaries will also be performed by absence/presence of HSCT after the start of this drug:

- Number of treatment cycles (continuous)
- Number of treatment cycles [1 cycle, 2 cycles, 3 cycles, 4 cycles, 5 cycles, 6 cycles, > 6 cycles]
- Number of treatment cycles [ $\leq$  3 cycles,  $\geq$  4 cycles]
- Dose amount in each cycle (continuous)
- Total dose amount (continuous)
- Dosing of  $> 1.8 \text{ mg/m}^2$  per cycle [absent, present] (Considered to be present, if there is a cycle of  $> 1.8 \text{ mg/m}^2$  per cycle during the treatment period.)

- **Pregnancy**

For the SAS, pregnancy status will be summarized:

- Pregnancy [absent, present] \* Pregnancy during the treatment period. Limited to cases in which information on pregnancy is collected

### **8.2.3. Safety analyses**

Adverse drug reactions (ADRs) and adverse events (AEs) that occurred in the following periods will be collected for summary: for ADRs and AEs other than VOD/SOS, those that occurred from the start of this drug to 28 days after the final dose of this drug will be collected; for ADRs and AEs of VOD/SOS in patients who did not undergo HSCT within 52 weeks after the start of this drug, those that occurred within 52 weeks after the start of this drug will be collected; for ADRs and AEs of VOD/SOS in patients who underwent HSCT within 52 weeks after the start of this drug, those that occurred within 52 weeks after the last HSCT will be collected. The listings will include all events reported in this survey.

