8.7. Observation Period

Observation period: The observation period will be 52 weeks for patients not undergoing HSCT within 52 weeks after the start of BESPONSA treatment or until 52 weeks following HSCT for patients undergoing it within 52 weeks after the start of BESPONSA treatment. For a patient starting BESPONSA treatment before 30 April 2020 who is transferred to another hospital during the observation period, the conclusion of the agreement on the implementation of this investigation should be requested to the hospital to which the patient has been transferred, and data from there should be collected to the extent possible.

(1) Treatment phase

From treatment initiation to Day 28 post-treatment: Safety (e.g., AEs) and efficacy (hematologic remission and survival)

(2) Follow-up phase

From Day 29 post-treatment to Week 52 (patients who did not undergo HSCT before Week 52) or 52 weeks after HSCT (patients who underwent HSCT before Week 52): Safety (VOD/SOS) and efficacy (survival)

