8.8.14. Adverse Events

Pertinent to safety assessment, the status of AEs during the period from the start of BESPONSA treatment to the end date of the observation period in the treatment phase (Day 28 post-treatment) will be confirmed, and the following information will be entered. For VOD/SOS, events during a period from the start of BESPONSA treatment to the end date of the observation period in the follow-up phase will be entered. When an AE is observed, the investigator should take an appropriate therapeutic action and promptly notify it to the sponsor. When the AE is related to BESPONSA, its course should be followed up until the AE or its sequelae resolve or become stable to the extent that is acceptable for the investigator and sponsor.

Also, further investigation should be separately conducted, if deemed necessary by sponsor for patients who experienced a serious adverse reaction, an unexpected adverse reaction or other adverse reactions not listed in the package insert.

- (1) Presence/absence of AE
- (2) Name of AE
- (3) Date of occurrence
- (4) CTCAE v4.0 Grade (worst grade)
- (5) Intervention
- (6) Seriousness
- (7) Outcome at the present
- (8) Causal relationship

Note: An AE is any and all unfavorable event (including clinically significant abnormal laboratory change) occurring in a patient after starting BESPONSA treatment regardless of causal relationship. A serious adverse event (SAE) is any unfavorable medical occurrence that results in death, is life-threatening, requires (or prolongs) hospitalization, causes persistent or significant disability/incapacity, results in congenital anomalies or birth defects, or is other conditions which represent significant health

PFIZER CONFIDENTIAL

Inotuzumab

B1931024 NON-INTERVENTIONAL STUDY PROTOCOL

Amended 8, 12 December 2023

hazards.

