## 2.1. Study Design

- **Target population**

*All patients who received this drug will be included in this survey.*

- **Survey period**

*The scheduled periods of this survey are as follows:*

*Survey period: From the date of launch of this drug to 5 years\**

*Registration period: From the date of launch of this drug to the time of lifting of approval conditions for all-case survey\**

*\*: Patients who started to receive this drug on or after May 1, 2020 will only be registered.*

The protocol may be changed to terminate the registration only period, but this change will not affect the SAP.

- **Observation period**

*Observation period: The observation period is to be 52 weeks for patients who did not undergo hematopoietic stem cell transplant (HSCT) within 52 weeks after the start of the treatment with this drug and up to 52 weeks after HSCT for patients who underwent HSCT within 52 weeks after the start of this drug. If patients who started to receive this drug on or before April 30, 2020 are transferred to another hospital during the observation period, the transferred hospitals will be requested to conclude a contract for the conduct of this survey, and the information at the transferred hospitals will be collected as much as possible.*

*[1] Treatment Period*

*From the start of treatment to Day 28 post-final dose: For assessments of safety (e.g., adverse events) and effectiveness (hematologic response, survival time)*

*[2] Follow-up period*

*For 52 weeks from 29 days after the final dose (for patients who did not undergo HSCT by 52 weeks after the start of treatment) or for 52 weeks after HSCT (for patients who underwent HSCT by 52 weeks after the start of treatment): For assessments of safety (VOD/SOS) and effectiveness (survival time)*

The starting point for the 52 week follow-up after HSCT is the day of the last HSCT performed within 52 weeks after the start of this drug.

- **Safety specification**

See Protocol Section 7.1.

- **Sample size and its rationale**

*Of the patients who have received this drug, a total of 176 patients with relapsed or refractory CD22 positive (CD22+) acute lymphocytic leukemia (ALL) will be included in the safety analysis set. In consideration of dropouts during the survey, 200 patients will be registered.*

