For ADRs that occurred in at least 10% of patients, number and proportion of patients with the ADRs will be summarized for each SOC and PT by category of timing of initial onset [ $< 4$  weeks after the start of treatment,  $\geq 4$  weeks to  $< 8$  weeks,  $\geq 8$  weeks to  $< 12$  weeks,  $\geq 12$  weeks to  $< 16$  weeks,  $\geq 16$  weeks to  $< 20$  weeks,  $\geq 20$  weeks to  $< 24$  weeks,  $\geq 24$  weeks].

In addition, time to event will be summarized as per Section 8.1.4 with event being the first onset of the AR. The analysis will be performed with the following specifications:

- Analysis set: SAS
- Handling of patients with no AR: Censored at 28 days after the final dose of this drug.
- Time points for rate estimation: Weeks 1, 2, 3, 4, 8, 12, 16, 20, and 24
- **Occurrence of adverse drug reactions by inclusion/exclusion in the safety analysis set**

For the population of patients whose case report form was collected, a listing of ADRs in patients excluded from the SAS will be prepared. In addition, excluded patients with ADRs will be summarized by SOC and PT.

- **VOD/SOS**

Events of VOD/SOS reported as AR will be analyzed. Events included in each analysis will not be limited to events of initial onset. Unless otherwise specified, VOD/SOS events will be summarized respectively for each of the following categories.

- VOD/SOS that occurred after the start of this drug (Use the SAS as the analysis set.)
- VOD/SOS that occurred with absence of HSCT after the start of this drug (Same as above): Here, "absence of HSCT" means that VOD/SOS occurred with no HSCT or occurred before any HSCT.
- VOD/SOS that occurred with presence of HSCT after the start of this drug (Patients in the SAS who underwent HSCT after the start of this drug will be analyzed)

**Occurrence of VOD/SOS:** The number of patients with VOD/SOS and its proportion will be summarized. Among the factors listed in "Details of adverse drug reactions" in Section 8.2.3.1, n and proportion will be summarized with respect to each of the following factors: Action taken [discontinuation, temporary suspension or dose reduction, none], Outcome [fatal, not recovered, recovered with sequelae, recovering, resolved/recovered, unknown], CTCAE Grade (1) [1, 2, 3, 4, 5, unknown], and CTCAE Grade (2) [ $< 3$ ,  $\geq 3$ , unknown].

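### SAP 8.2.3 gives transplanted patients a VOD/SOS window that, as printed, opens at the last HSCT and so omits events from drug start up to that transplant

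*SAP*

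**What the plan says.** SAP 8.2.3 opens with one sentence that fixes which adverse events and adverse drug reactions are taken into the summaries. It has three clauses:

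- Events other than VOD/SOS: "those that occurred from the start of this drug to 28 days after the final dose of this drug will be collected".
- VOD/SOS in patients with no HSCT within 52 weeks: "those that occurred within 52 weeks after the start of this drug will be collected".
- VOD/SOS in patients with an HSCT within 52 weeks: "those that occurred within 52 weeks after the last HSCT will be collected".

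The next sentence exempts the listings, which show every reported event.

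Four other places bear on the third clause:

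- Protocol 8.7 sets the observation period for transplanted patients: "until 52 weeks following HSCT for patients undergoing it within 52 weeks after the start of BESPONSA treatment".
- Protocol 8.8.14 has the CRF record VOD/SOS "from the start of BESPONSA treatment to the end date of the observation period in the follow-up phase".
- SAP 2.1 starts the 52-week follow-up after transplant at "the day of the last HSCT performed within 52 weeks after the start of this drug".
- SAP 8.2.3.1 summarises VOD/SOS overall from drug start in the safety analysis set. It adds an absence-of-HSCT category for VOD/SOS that "occurred with no HSCT or occurred before any HSCT", and a category for VOD/SOS with HSCT.

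**The concern.** The first two clauses run from drug start. The third names only the last HSCT. VOD/SOS that arises after dosing but before transplant, or between a first and a later transplant, has no place in the printed window. The first clause does not rescue it, because that clause excludes VOD/SOS.

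The sentence sets the numerator for the event on which the survey was sized. If it were programmed as printed, the tables would under-count VOD/SOS in transplanted patients before their last transplant. They would also follow transplanted and non-transplanted patients over windows with different starting points. A reader of the report could not tell which window lay behind the published proportion.

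**Working it through.** **1. Does the printed clause open at the last HSCT?** The SAP uses the same construction elsewhere for a window that opens at the named date. The second clause of the same sentence counts from drug start. Section 6.1 defines early death as death within 100 days after the first HSCT. Where both ends are meant to be stated, the sentence states them, as in its first clause. On the SAP's own usage, the third window runs from the last HSCT to 52 weeks later.

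**2. The passages side by side**

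| Place | Start of VOD/SOS window, transplanted patients | End |
|---|---|---|
| SAP 8.2.3, as printed | last HSCT | 52 weeks after it |
| Protocol 8.8.14 with 8.7 | drug start | 52 weeks after HSCT |
| SAP 2.1 | observation runs from drug start | 52 weeks after the last HSCT done within 52 weeks of drug start |
| SAP 8.2.3.1, overall category | drug start | not restated |

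Three outputs in SAP 8.2.3.1 need events that the printed window removes:

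- the absence-of-HSCT category and the matching row of the HSCT table, which count VOD/SOS before HSCT;
- onset timed from the *first* HSCT, which needs events between a first and a later transplant;
- onset rates every 4 weeks from Week 4 to Week 52. A transplanted patient whose only VOD/SOS came before the last HSCT would be treated there as event-free and censored.

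**3. Two illustrations (dates assumed)**

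- *HSCT at weeks 20 and 40.* The printed window is weeks 40 to 40 + 52 = 92. The window from drug start is weeks 0 to 92. VOD/SOS at week 10 (before any HSCT) or week 22 (two weeks after the first) is counted under the second and dropped under the first.
- *HSCT at weeks 20 and 70.* Under SAP 2.1 the week-70 transplant does not count, and observation ends at 20 + 52 = 72. Under 8.2.3 as printed, the window is weeks 70 to 122. Everything before week 70 drops out, and planned collection stops at week 72. The missing limit therefore moves the window.

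**4. Effect on the proportions**

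- *Absence of HSCT.* The denominator is the whole safety analysis set. Patients transplanted within 52 weeks remain in it but cannot add a pre-HSCT event, so the proportion can only be biased downward.
- *Overall.* The table counts patients. A patient is lost only if every VOD/SOS event came before the last HSCT. With *k* such patients and 176 analysed, the proportion falls by *k*/176: 0.57 points for *k* = 1, 1.1 for *k* = 2, 2.3 for *k* = 4. These values of *k* are illustrative, and the documents give none.
- *HSCT after drug start, as a risk factor.* The not-transplanted group is counted from drug start and the transplanted group from the last HSCT. The transplanted group's proportion, and its ratio to the other group, are pulled down.

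**5. The stated sample-size figures.** With 12.3% overall, relative risk 3.0 and a 1:1 split, the low rate is 2 × 12.3%/(1 + 3) = 6.15% and the high rate is 18.45%. With 88 per group and two-sided alpha 0.1:

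- null standard error √(2 × 0.123 × 0.877/88) = 0.0495;
- alternative standard error √((0.1845 × 0.8155 + 0.0615 × 0.9385)/88) = 0.0486;
- power Φ((0.123 − 1.645 × 0.0495)/0.0486) = 80.4%.

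The plan's figure reproduces. None of its inputs depends on the clause, so correcting the clause leaves it unchanged.

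**The case against.** The best reply is that the clause is an end limit in shorthand. Protocol 8.7 and SAP 2.1 both treat 52 weeks after HSCT as the close of a period that began at drug start, Protocol 8.8.14 states that start, and SAP 8.2.3.1 specifies outputs that make no sense under the literal reading. A programmer working through 8.2.3.1 would probably notice. SAP 2.1 also already says which transplant is last. Much of this stands: the intended meaning is very likely the end limit, and it can be recovered. But 8.2.3 is the only place that says which events enter the summaries. A rule that gives a wrong numerator when followed exactly should not depend on being overridden by inference.

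A reader might infer three stronger things that the documents do not support:

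- *That VOD/SOS data are lost.* They are not. The CRF records VOD/SOS from drug start and the listings are unrestricted, so only the summaries are exposed.
- *That a particular number of events disappears, with a stated fall in incidence or power.* No document gives the share of VOD/SOS that precedes the last HSCT. The tables count patients, so subtracting events overstates the loss for anyone who also has a later event. SAP 4.1 treats tests as exploratory with no fixed significance level.
- *That a transplant after week 52 lengthens the window.* As printed it shifts the window, and planned collection ends with the observation period in any case.

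**Conclusion.** The point holds as a drafting defect in an operative rule. As printed, the window for transplanted patients excludes VOD/SOS between drug start and the last HSCT, and it contradicts Protocol 8.8.14 and SAP 8.2.3.1. It becomes an analysis error only if the sentence is programmed literally. The overall and absence-of-HSCT proportions would then be biased downward and the comparison by HSCT after drug start distorted. The direction follows from the text. The size does not, beyond 0.57 percentage points of overall incidence per affected patient, assuming 176 patients analysed. It should be corrected because it governs the survey's key safety event, but it does not call the data or the survey's size into question.

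**What to change.** In SAP 8.2.3, replace the third clause so that VOD/SOS in patients with an HSCT within 52 weeks is collected *from the start of this drug up to 52 weeks after* "the day of the last HSCT performed within 52 weeks after the start of this drug". This supplies the missing start and carries over the Section 2.1 limit on which transplant counts. It brings the clause into line with Protocol 8.7 and 8.8.14 and with the outputs in SAP 8.2.3.1.

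The cost is one SAP sentence and a check that the table programs use the same window. No new data, protocol change or revised sample-size figure is needed.
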